3. PROTOCOL SUMMARY

3.1. Synopsis

Name of Sponsor/Company: US WorldMeds, LLC

Name of Investigational Product: Lofexidine hydrochloride (HCl) (LUCEMYRATM)

Name of Active Ingredient: Lofexidine

Title of Study: A Randomized, Double-Blind, Placebo-Controlled Pilot Study to Evaluate the Safety and Effectiveness of LUCEMYRA in the Treatment of Opioid Withdrawal During an Opioid Taper in Subjects with Chronic Non-Cancer Pain

Study Center(s): 7

•	
Studied Period (years):	Phase of Development: 2
Estimated date first subject enrolled: July 2019	
Estimated date last subject completed: December 2019	

Objectives and Assessments:

Objectives	Endpoints	
Primary		
• Evaluate the safety and tolerability of LUCEMYRA versus placebo when used during an opioid taper in subjects with chronic non-cancer pain	AE reports, clinical laboratory assessments, monitoring of DILI, vital signs, C-SSRS	
Secondary		
• Estimate the difference between treatment groups in measures related to opioid withdrawal and completion of opioid discontinuation when tapered	Taper completion status, reduction in opioid use, urine drug screen, COWS, MCGI-R, MCGI-S, SOWS-Gossop, SOWS-H	
• Estimate the difference between treatment groups in measures of effectiveness in pain relief, quality of life, and treatment satisfaction	EQ-5D-5L, HADS, ISI, NRS, SF-36, Subject Satisfaction, and use of rescue medication for pain	

AE = adverse event; COWS = Clinical Opiate Withdrawal Scale; C-SSRS = Columbia-Suicide Severity Rating Scale; DILI = drug-induced liver injury; EQ-5D-5L = EuroQol 5-Dimension 5-Level; HADS = Hospital Anxiety and Depression Scale; ISI = Insomnia Severity Index; MCGI-R = Modified Clinical Global Impression – Rater Version; MCGI-S = Modified Clinical Global Impression – Subject Version; NRS = Numeric Rating Scale; SF-36 = Short Form Health Survey– 36 items; SOWS-Gossop = Short Opiate Withdrawal Scale of Gossop; SOWS-H = Subjective Opiate Withdrawal Scale of Handelsman

Rationale: A significant portion of the public health issues related to long-term prescription opioid use are thought to arise from the difficulty of opioid discontinuation. Following the approval of LUCEMYRA for mitigation of opioid withdrawal symptoms to facilitate abrupt opioid discontinuation in adults, its use in the setting of an opioid taper has become a topic of interest among clinicians managing physical opioid dependence in chronic pain patients.

Enhanced treatment options for emerging opioid withdrawal symptoms during opioid taper regimens may permit development of more efficient tapering protocols, which in turn would have significant

impact on reducing risk to patients on chronic opioids and may positively impact health economic outcomes.

There is a notable lack of well-controlled data on the opioid withdrawal syndrome during an opioid taper in chronic non-cancer pain patients. Gradually tapering a patient's opioid dose with small reductions in dose over a prolonged period of time is a practice inherently designed to mitigate the potential for opioid withdrawal. LUCEMYRA's effectiveness in treating opioid withdrawal symptoms has been established in the setting of abrupt opioid discontinuation; however, has not been thoroughly evaluated in the setting of an opioid taper. Opioid tapers are often conducted over several weeks, if not months, resulting in the potential for at least cumulative use of LUCEMYRA for beyond 14 days. A clinical trial is necessary to assess for a signal of serious hypotension, bradycardia, syncope, hepatotoxicity, or rebound hypertension, or identify potential unexpected serious risks of long-term use of LUCEMYRA in the setting of an opioid taper as the majority of the existing safety data for LUCEMYRA is on less than 14 days of use. This pilot study is intended to inform critical study design elements for a future pivotal study to assess the safety and efficacy of LUCEMYRA for use beyond 14 days in the setting of an opioid taper.

Methodology:

This is a pilot, multicenter, randomized, double-blind, placebo-controlled, outpatient clinical trial to assess the safety and tolerability, and to estimate the effectiveness of LUCEMYRA for mitigating the symptoms of opioid withdrawal in the setting of an opioid taper in subjects with chronic non-cancer pain.

After a Screening period of up to 28 days, subjects will begin a planned 14-day complete taper of their pre-study opioid and will be randomly assigned (1:1) to either LUCEMYRA or matching placebo. Study drug will be administered through the opioid taper and for 5 days after the opioid taper is completed. Study drug will then be tapered over a 4-day period for a total of approximately 21 days exposure to study drug (Figure 1).

Day 1 dosing with study drug will begin in the clinic as 1 tablet (LUCEMYRA 0.18 mg/tablet or matching placebo) 4 times per day (QID) for a total daily dose of LUCEMYRA 0.72 mg or matching placebo. Subjects will be instructed to take their study drug in the morning upon awakening and then every 5 to 6 hours thereafter. Doses should be taken 5 to 6 hours apart and no more than 4 times per day. At the Day 1 Visit (Visit 1), the Investigator should schedule a phone call with the subject, to occur prior to the second dose of study drug on Day 2, to review the subject's at-home vital signs measurement and how the subject is feeling. The subject will be instructed to contact the site if they experience signs or symptoms of hypotension, bradycardia, or orthostasis (eg, lightheadedness, slow heart rate, dizziness, feeling faint at rest or when standing up) while continuing to dose at home on Day 1. If the subject contacts the site on Day 1 reporting these symptoms, the Investigator should consider reducing the planned first daily dose on Day 2.

On Day 2 the subject will be instructed to take 2 tablets QID (LUCEMYRA 1.44 mg/day or matching placebo), unless Day 1 dosing was not well-tolerated. The subject should contact the site if they experience signs or symptoms of hypotension, bradycardia, or orthostasis (eg, lightheadedness, slow heart rate, dizziness, feeling faint at rest or when standing up) after the first daily dose. The Investigator will contact the subject on Day 2, prior to the second dose of the day, to review the subject's at-home vital signs measurement and how the subject is feeling. The Investigator should discuss with the subject any changes to dosing of study drug. Dosing instructions may include an increase to 3 tablets per dose due to subject report of intolerable opioid withdrawal symptoms, or a reduction back to 1 tablet per dose, due to intolerability of study drug.

On Day 3 and beyond, dosing will be at the discretion of the Investigator, as guided by subject tolerability of study drug and opioid withdrawal symptoms.

The dose of study drug may be increased to manage opioid withdrawal symptoms. If an increased dose of study drug is not well tolerated, the dose can be decreased. A single dose of study drug should not exceed 4 tablets (LUCEMYRA 0.72 mg or matching placebo). The total daily dose of study drug should not exceed 4 tablets QID (LUCEMYRA 2.88 mg/day or matching placebo).

Subjects will be tapered from their baseline total daily dose of opioid (calculated as morphine equivalent dose [MED]) over a 14-day period. The opioid dose will be decreased as close as possible to achieve the following dose reduction targets: 50% from the baseline MED beginning with the last dose of the day on Day -1, an additional 25% of the baseline MED beginning on Day 6, and a final 25% of the baseline MED (to dose of zero) beginning on Day 13. Reminders for opioid dose reduction may be done via phone, text, or other electronic message.

Opioid dosing to achieve the required dose reductions in accordance with the protocol defined taper must be planned during Screening. Any changes in opioid prescription to facilitate the protocol taper should be discussed with the subject's primary pain physician, when applicable, and prescribed in advance of randomization. The Investigator should work with a preferred pharmacy informed about the subject's participation in a clinical trial in order to fulfill prescribing needs to facilitate the opioid taper. Opioid prescriptions should be written to accommodate the planned taper, as specified per protocol in Section 9.3. The subject's baseline opioid regimen and MED calculation as well as the opioid regimen planned to achieve each taper step should be submitted to and approved by the Medical Monitor prior to Day -1.

Non-opioid medications taken during the study should be in compliance with the allowed concomitant treatments in Section 9.4. Opioid dose reductions may not occur on a Friday or Saturday unless clinic can accommodate subjects on Saturday and Sunday. Qualified study personnel at the clinic should call the subject the day after the opioid dose is decreased (except on Day 1 since the subject will come to the clinic) to review the subject's at-home vital signs measurement and how the subject is feeling. Upon review by the Investigator or designee, changes to dosing of study drug should also be discussed with the subject if applicable.

Subjects who experience intolerable withdrawal symptoms, despite increasing their dose of study drug to the maximum tolerated dose (not to exceed 4 tablets QID), will be allowed to pause the opioid taper once. Pausing the opioid taper includes either a return to the last stable opioid dose for the remainder of the current opioid dose reduction period, or remaining on the current opioid dose instead of reducing at the next scheduled reduction, resulting in an overall extended opioid taper period and study duration. For example, if a subject experiences intolerable withdrawal at the second opioid dose reduction step [25% of baseline MED], they may either 1) return to the first reduction dose [50% of baseline MED]) or, 2) when the withdrawal persists until the next scheduled reduction step, they may remain for longer at the current opioid dose [25% of baseline MED]. In both cases, the taper must be resumed following the single pause in accordance with the protocol schedule. Subjects who cannot or are unwilling to continue the opioid taper after one pause will be discontinued from the study.

Decisions on whether to pause the opioid taper will be based on subject request and an evaluation (in clinic or over the phone) of the subject's status by the Investigator. Subjects may request to pause the opioid taper due to opioid withdrawal symptoms. If the subject's last COWS score is \geq 5 OR if based on i) the Investigator's discussion with the subject, ii) review of ongoing subject-reported withdrawal related AEs, and iii) most recent scores for subject reported withdrawal scales, the subject's desire to pause the taper is related primarily to opioid withdrawal discomfort in the Investigator's opinion, then the taper may be paused. In the event that the Investigator assesses the subject's desire to pause the taper to be primarily related to pain, a taper pause will not be permitted; however, if the subject is willing to continue the per protocol taper, recommended modifications to their concurrent pain management plan should be discussed and recorded. Subjects unwilling to continue the per protocol taper, a single pause should be discontinued from the study.

Study drug dosing for an opioid taper pause will remain at the discretion of the Investigator, as guided by subject tolerability of study drug and opioid withdrawal symptoms. The dose of study drug can be increased or decreased as needed.

Dosing of study drug will continue for 5 days after the last opioid dose. Study drug will then be tapered over an additional 4 days (Section 9.2.3).

Subjects will be given a diary to take home and will use it to complete daily questionnaires regarding withdrawal and other symptoms, average and worst daily pain, record opioid and study drug administration and concomitant treatment use (including use of medication for pain or opioid withdrawal symptoms).

Subjects will take their blood pressure and heart rate at home using a vital sign monitor. At home readings will be collected during phone calls conducted by study staff after each opioid dose reduction and twice daily (morning and evening) during the 4-day study drug taper through the End of Study (EOS) Visit. Subjects will record readings in their diary.

Subjects will return to the clinic on Day 3, Day 8, and then on a weekly basis following randomization during study drug administration for assessments. With the exception of Day 1 (Visit 1), clinic visits can occur \pm 1 day from the study-specified timepoint. Subjects will return to the clinic approximately 7 days after their last dose of study drug. At 30 days following the last dose of study drug, subjects will receive a telephone call for a safety follow-up and assessment of the subject's current opioid usage, after which their participation in the study will be complete.

Subjects who prematurely discontinue the study will be instructed to taper study drug as described in Section 9.2.3 and to complete the at-home assessments for the study drug taper period (Table 4 or Table 5). Once discontinued, subjects may not re-enter the study.

Number of Subjects:

60 subjects (30 LUCEMYRA, 30 placebo)

A sample size of 30 subjects per group provides adequate precision for the estimated treatment difference for the incidence of adverse withdrawal events during opioid taper. Precision of the estimated difference is quantified by the width of the 95% confidence interval for the treatment difference.

Diagnosis and Main Criteria for Eligibility:

Inclusion Criteria

- 1. Subject can provide written informed consent.
- 2. Subject is willing and able to comply with scheduled visits, treatment plan, laboratory tests, and other study procedures.
- 3. Chronic non-cancer pain diagnosis such as low back pain, chronic neck pain, osteoarthritis, and prolonged post-surgical pain with daily pain for a minimum of 6 months.
- 4. Men and women at least 18 years of age at the time of signing informed consent.
- 5. Self-reported use of prescribed oral opioid medication(s), taken as tablets, pills, or capsules, of at least 50 morphine mg equivalent (MME) but no higher than 240 mg MME daily or near daily (≥5 days per week) for at least 12 weeks and seeking to discontinue their opioid medication. MMEs must be calculated using conversion factors recommended by the Center for Disease Control and Prevention to confirm the MED for the day is between 50-240 MME, including both breakthrough and around-the-clock pain medications, at Screening. The

Medical Monitor must review and approval all baseline opioid use consumption and planned taper dosing regimens prior to Day -1.

- 6. Willing to be treated with non-opioid treatments for pain (in addition to opioid being tapered) for the duration of the study.
- 7. Subject agrees to follow the opioid taper plan, both in terms of the planned changes in the doses of opioid medications and the schedule for when opioid dose reductions will be made, as outlined by the Investigator and approved by the study Medical Monitor.
- 8. Subject agrees to partner with his or her pain physician on a subject-centered pain management program during the study.
- 9. If the subject is not normally a patient at the clinic, the subject's normal pain physician must sign an attestation that the physician agrees to resume the subject's pain management care following the study.
- 10. In generally good health, in the opinion of the Investigator, other than the underlying chronic pain syndrome at Screening based upon the results of a medical history, physical examination, 12-lead electrocardiogram, and laboratory profile.
- 11. Subject agrees to abstain from use of alcohol during the study.
- 12. Women of childbearing potential must have a negative pregnancy test at Screening.
- 13. Non-pregnant, non-lactating women who are postmenopausal, naturally or surgically sterile, or who agree to use acceptable contraceptive methods throughout the course of the study. Postmenopausal is defined as at least 12 months of amenorrhea, or at least 6 weeks following surgical menopause, defined as bilateral oophorectomy, tubal ligation, or hysterectomy. If of childbearing potential, subject must have been using birth control for at least 30 days and must agree to use one of the following methods of birth control:
 - Oral contraceptives
 - Patch
 - Barrier method (diaphragm, sponge, or condom) with spermicidal preparations
 - Intrauterine contraceptive system
 - Levonorgestrel implant
 - Medroxyprogesterone acetate contraceptive injection
 - Complete abstinence from sexual intercourse
 - Hormonal vaginal contraceptive ring; surgical sterilization, or partner sterile
- 14. If male, must agree to use one of the birth control methods listed in inclusion criterion 13 throughout the entire study period and for 90 days after the last dose of study drug. Must not donate sperm for 90 days after the last dose of study drug.
- 15. Able to speak, write, and understand English, understand the consent form, and be able to effectively communicate with the study staff.

Exclusion Criteria

- 1. Has a primary diagnosis of complex regional pain syndrome, central neuropathic pain, somatoform pain syndromes, acute nerve root compression, any acute or progressive infectious, inflammatory, or neurological process.
- 2. Liver disease that requires medication or medical treatment, and/or aspartate aminotransferase (AST) or alanine aminotransferase (ALT) levels greater than 3 times the upper limit of normal (ULN).
- 3. Gastrointestinal or renal disease, which would significantly impair absorption, metabolism or excretion of study drug, or would require medication or medical treatment.
- 4. Has a diagnosis of epilepsy or history of seizures.
- 5. Has clinically significant abnormal laboratory value(s).
- 6. Self-reported or evidence of opioid use disorder (OUD) or other substance use disorder within last 12 months prior to Screening using the Sponsor-provided Mini-International Neuropsychiatric Interview.
- 7. Urine toxicology screen positive for any illicit or non-prescribed opioid drugs prior to randomization.
- 8. Taking prescription methadone, buprenorphine, fentanyl rapid acting products, tapentadol, tramadol, butorphanol, meperidine, or levorphanol for any reason.
- 9. Known or suspected pregnancy, planned pregnancy, or lactation.
- 10. Any of the following cardiovascular abnormalities at Screening and before randomization:
 - a. Resting heart rate ≥ 105 bpm or <55 bpm or symptomatic bradycardia;
 - b. Resting systolic blood pressure ≥ 160 mmHg or < 95 mmHg or symptomatic hypotension;
 - c. Resting diastolic blood pressure \geq 90 mmHg or <65 mmHg;
 - d. Clinically significant abnormal electrocardiogram (eg, second- or third-degree heart block, uncontrolled arrhythmia; QT corrected by heart rate by Fridericia's method (QTcF) of ≥450 msec or a history of QT interval prolongation;
 - e. New York Heart Association class III or IV; or
 - f. History of myocardial infarction within 6 months of Screening.

Medications taken for stable hypertension are permitted when dose/regimen has been consistent for a minimum of 3 month prior to screening.

- 11. Any severe or unstable psychiatric disorder including post-traumatic stress disorder, schizophrenia, bipolar disorder, major depression, substance abuse, or suicidality as determined by the Investigator.
- 12. Subject answers "yes" to "suicidal ideation" in prior 24 months to any items 1 through 5 on the C-SSRS, or subject answers "yes" to any lifetime "suicidal behavior" item on the C-SSRS.
- 13. Requires any of the following medications currently or within the past 30 days:
 - a. Alpha-2 adrenergic agonists
 - b. Antiarrhythmics
 - c. Barbiturates

Study Drug Dosage and Mode of Administration:

LUCEMYRA 0.18-mg tablets or placebo taken orally. A single dose of study drug should not exceed 4 tablets (LUCEMYRA 0.72 mg or matching placebo). The total daily dose of study drug should not exceed 4 tablets QID (LUCEMYRA 2.88 mg/day or matching placebo).

Duration of Treatment and Study:

The study duration for each subject will be up to 85 days. The Screening period is up to 28 days, the study drug administration period (including a 4-day study drug taper) is 21 to 27 days (the latter for those requiring an extended opioid taper), and a 30-day safety follow-up period.

Criteria for Evaluation:

Safety:

The following safety endpoints will be assessed:

- Number and percent of subjects reporting treatment-emergent adverse events (TEAEs) by system organ class and preferred term.
- Number and percent of subjects reporting treatment-emergent serious adverse events (SAEs) by system organ class and preferred term.
- Number and percent of subjects reporting TEAEs resulting in study drug discontinuation by system organ class and preferred term.
- Change in vital signs from Baseline to each scheduled evaluation.
- Change in clinical laboratory values from Baseline to each scheduled evaluation.
- Percentage of subjects with treatment-emergent ALT, AST, or alkaline phosphatase >3 × ULN and total bilirubin >2.0 mg/dL at the same evaluation.
- Percentage of subjects identified as suicide risk with C-SSRS.

Effectiveness:

The following effectiveness endpoints will assess withdrawal symptoms and pain:

- Percentage of subjects who successfully complete each scheduled dose reduction and the opioid taper to complete opioid discontinuation, with or without a pause.
- Change in COWS from Baseline to peak value and to each scheduled evaluation.
- Change in SOWS-H from Baseline to peak value and to each scheduled evaluation.
- Change in SOWS-Gossop from Baseline to peak value and to each scheduled evaluation.
- MCGI-R by each scheduled evaluation.
- MCGI-S by each scheduled evaluation.
- Time to study drug discontinuation.
- Change in daily opioid dose, expressed as MED, and as a percentage of the baseline MED.
- Number of non-opioid concomitant medications for withdrawal symptoms used by study day.
- Change in average and worst daily pain from Baseline to peak value as measured by the NRS.
- Change in EQ-5D-5L from Baseline to each scheduled evaluation.
- Change in SF-36 from Baseline to each scheduled evaluation.
- Change in ISI from Baseline to each scheduled evaluation.
- Change in HADS from Baseline to each scheduled evaluation.

Statistical Methods:

The treatment group difference in proportions will be summarized descriptively with a 95% confidence interval. The 95% confidence interval will be calculated based on the normal approximation for the binomial distribution, using the Wald continuity correction. In addition, the treatment group difference will be tested with Cochran-Mantel-Haenszel (CMH) test stratified by total opioid dose (<90 MED, \geq 90 MED.

The treatment group difference for mean change will be summarized descriptively with 95% confidence intervals. The 95% confidence intervals for the treatment group differences will be calculated within the framework of analysis of covariance (ANCOVA). The ANCOVA will have treatment and total opioid dose (<90 MED, \geq 90 MED) as fixed factors and baseline as covariate. In addition, the treatment group difference will be tested within the ANCOVA framework.

[figure not shown]
Safety data will be summarized with descriptive statistics. Adverse events (AEs) will be categorized by system organ class and preferred term with the Medical Dictionary for Regulatory Activities.

An interim analysis will be conducted after approximately 30 subjects have completed or discontinued the study. Based on the interim analysis, the study may be stopped for futility but will not be stopped for a positive demonstration of effectiveness. Therefore, no adjustment of Type I error is necessary.

Study Schedule with Opioid Taper Pause

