6.4. Assessment Tools Used to Achieve Objectives

The assessment tools used to achieve the study objectives are presented in Table 7. Effectiveness and safety endpoints, based on these assessment tools, are defined in Section 7.2.

Objective	Assessment Tools
Primary Objective	
Evaluate the safety and tolerability of LUCEMYRA versus placebo when used during an opioid taper in subjects with chronic non-cancer pain	AE reports, clinical laboratory assessments, monitoring of DILI, vital signs, and C-SSRS
Secondary Objectives	
Estimate the difference between treatment groups in measures related to opioid withdrawal and completion of opioid discontinuation when tapered	Taper completion status, reduction in opioid use, urine drug screen, COWS, MCGI-R, MCGI-S, SOWS-Gossop, SOWS-H
Estimate the difference between treatment groups in measures of effectiveness in pain relief, quality of life, and treatment satisfaction	EQ-5D-5L, HADS, ISI, NRS, SF-36, subject satisfaction, and use of rescue medication for pain

 Table 7:
 Assessment Tools Used to Achieve Objectives

AE = adverse event; COWS = Clinical Opiate Withdrawal Scale; C-SSRS = Columbia-Suicide Severity Rating Scale; DILI = drug-induced liver injury; EQ-5D-5L = EuroQol 5-Dimension 5-Level; HADS = Hospital Anxiety and Depression Scale; ISI = Insomnia Severity Index; MCGI-R = Modified Clinical Global Impression – Rater Version; MCGI-S = Modified Clinical Global Impression – Subject Version; NRS = Numeric Rating Scale; SF-36 = Short Form Health Survey – 36 Items; SOWS-Gossop = Short Opiate Withdrawal Scale of Gossop; SOWS-H = Subjective Opiate Withdrawal Scale of Handelsman

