Non-opioid medications taken during the study should be in compliance with the allowed concomitant treatments in Section 9.4. Opioid dose reductions may not occur on a Friday or Saturday unless clinic can accommodate subjects on Saturday and Sunday. Qualified study personnel at the clinic should call the subject the day after the opioid dose is decreased (except on Day 1 since the subject will come to the clinic) to review the subject's at-home vital signs measurement and how the subject is feeling. Upon review by the Investigator or designee, changes to dosing of study drug should also be discussed with the subject, if applicable.

Subjects who experience intolerable withdrawal symptoms despite increasing their dose of study drug to the maximum tolerated dose (not to exceed 4 tablets QID) will be allowed to pause the opioid taper once. Pausing the opioid taper includes either a return to the last stable opioid dose for the remainder of the current opioid dose reduction period, or remaining on the current opioid dose instead of reducing at the next scheduled reduction, resulting in an overall extended opioid taper period and study duration. For example, if a subject experiences intolerable withdrawal at the second opioid dose reduction step [25% of baseline MED], they may either 1) return to the first reduction dose [50% of baseline MED]) or, 2) when the withdrawal persists until the next scheduled reduction step, they may remain for longer at the current opioid dose [25% of baseline MED]. In both cases, the taper must be resumed following the single pause in accordance with the protocol schedule. Subjects who cannot or are unwilling to continue the opioid taper after one pause will be discontinued from the study.

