12.2.3. Recording Adverse Events

All AEs and details for the events will be recorded in the subject's source document and eCRF. An AE should be documented in terms of a medical diagnosis and reported in standard medical terminology when possible. When this is not possible, the AE should be documented in terms of signs and/or symptoms observed or reported. It is important for the Investigator to only record 1 AE per line on the eCRF. Combination events (eg, nausea/vomiting), should be entered as 2 events.

The Investigator must determine the intensity of the AE as defined by:

- Mild: no medical interventions required, short lasting discomfort, and does not interfere with subject's daily activities
- Moderate: activity may be limited, and subject may require minimal medical therapy, intervention, or assistance
- Severe: definitely limits subject's daily activity that may require hospitalization and or intervention/therapy assess whether or not the study drug caused the AE

The Investigator will record whether the AE or AEs led to discontinuation of the subject from the study, record the outcome of the AE (unresolved, resolved, resolved with sequelae, death, or unknown), and determine if the AE is serious.

For this study, AEs and SAEs will be collected beginning with the start of dosing on Day 1 and will end 30 days after the last dose of study drug.

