13.4.2. Safety Analysis

All safety analyses will be performed on the Safety Population using the treatment actually received. All safety summaries will be descriptive; no statistical testing will be performed.

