13.4.2.1.1. Adverse Events

A TEAE is defined as an AE with an onset that occurs after receiving study drug, or a continuing AE diagnosed prior to the date of first dose of study drug, which increases in severity after the start of dosing. AEs will be categorized by system organ class and preferred term with the Medical Dictionary for Regulatory Activities.

Summary tables for TEAEs will include number and percent of subjects experiencing TEAEs by system organ class and preferred term. If a subject has more than 1 TEAE that codes to the same preferred term, the subject will be counted only once for that preferred term. Similarly, if a subject has more than 1 TEAE within a system organ class category, the subject will be counted only once in that system organ class category.

The following TEAE summaries will be provided:

- Overall summary of TEAEs
- TEAEs by system organ class and preferred term
- Drug-related TEAEs by system organ class and preferred term
- TEAEs by system organ class, preferred term, and severity

Serious TEAEs and TEAEs leading to study drug discontinuation will be identified.

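### TEAEs are summarised only as crude percentages of subjects, with no exposure summary beside them, although time on study drug is itself compared between arms

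*Combined protocol and SAP*

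**What the plan says.** - **Endpoint and tables.** The Synopsis and Section 7.2.1 list seven safety endpoints, the first being "Number and percent of subjects reporting treatment-emergent adverse events (TEAEs) by system organ class and preferred term". Section 13.4.2.1.1 carries this into the analysis: "Summary tables for TEAEs will include number and percent of subjects experiencing TEAEs by system organ class and preferred term". Its list of summaries covers overall, by class and term, drug-related, and by severity. None uses person-time or time to first event, and the supplied text has no extent-of-exposure table.
- **Role.** The primary objective is safety and tolerability versus placebo. Section 6.4 gives its tools as "AE reports, clinical laboratory assessments, monitoring of DILI, vital signs, and C-SSRS". No single primary endpoint is named.
- **Testing.** Section 13.4.2: "All safety summaries will be descriptive; no statistical testing will be performed".
- **Time on drug.** "Time to study drug discontinuation" is an effectiveness endpoint. Section 13.4.1.4 presents it by Kaplan-Meier curve and log-rank test. Section 9.3: "Subjects who cannot or are unwilling to continue the opioid taper after one pause will be discontinued from the study". Section 8.5 adds intolerable AEs as a reason to leave. Planned dosing is 21 days, or 27 with a taper pause (Section 7.4).
- **AE window.** "A TEAE is defined as an AE with an onset that occurs after receiving study drug", with no cut-off at the last dose. Collection "will end 30 days after the last dose of study drug" (Section 12.2.3).
- **Early leavers.** Sections 7.1 and 8.6 instruct them to taper study drug, which takes 4 days under Section 9.2.3.

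**The concern.** A percentage of subjects with an event depends on both how often events occur and how long subjects are exposed. The rules for leaving the trial tie exposure to outcome. A drug that controls withdrawal may keep its subjects on treatment longer, and a badly tolerated one may lose them sooner. In the first case an arm with the same daily event rate looks worse. In the second, part of a higher daily rate is hidden.

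This bears on the trial's purpose. The Synopsis rationale says most existing safety data cover less than 14 days of use, and it seeks signals such as hypotension, bradycardia, syncope and rebound hypertension with longer use. A crude percentage does not show how many subjects in each arm passed 14 days, or whether an event arose on drug or after stopping.

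**Working it through.** **1. The plan's own precision figure.** Section 13.2 gives half-widths of 0.24 (20 per group) and 0.17 (40 per group) for a difference of 0.2. The text does not state the two proportions, and Figure 2 is not available. Using 1.96 × √[(p1q1 + p2q2)/n] without continuity correction, the pair 0.10 and 0.30 reproduces both:
- n = 20: 1.96 × √(0.30/20) = 0.240
- n = 40: 1.96 × √(0.30/40) = 0.170
- planned n = 30: 1.96 × √(0.30/30) = 0.196, or about 20 points

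**2. Inputs for the distortion.** From the plan: 21 days on drug for completers, a 4-day drug taper after early discontinuation, and AE collection for 30 days after the last dose. The plan gives no stopping or event rates, so these are assumptions: a proportion d stops, spread evenly over Days 3-17; d = 0.5-0.6 in one arm and 0.2 in the other; constant daily hazard h = 0.02-0.05.

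**3. Formula.**

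Crude risk = d × mean over t = 3..17 of [1 − exp(−h·T(t))] + (1 − d) × [1 − exp(−h·(21 + w))], where T(t) = min(t + k, 21) + w.

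Here k = 4 if the drug taper after stopping is counted and 0 if not. w = 30 if the hazard continues through follow-up and 0 if events arise only on drug.

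**4. Mean days on drug.** Stoppers average 10 days without the taper and 14 with it.
- Without taper: 0.6 × 10 + 0.4 × 21 = 14.4; 0.5 × 10 + 0.5 × 21 = 15.5; 0.2 × 10 + 0.8 × 21 = 18.8
- With taper: 16.8, 17.5 and 19.6

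**5. False difference with equal hazards** (better-retained arm minus the other, percentage points):

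| Stopping | h | On drug, no taper | On drug, with taper | Taper and 30-day window |
|---|---|---|---|---|
| 50% v 20% | 0.02 | 4.9 | 3.0 | 1.7 |
| 50% v 20% | 0.03 | 6.4 | 3.9 | 1.6 |
| 50% v 20% | 0.05 | 8.1 | 4.8 | 1.1 |
| 60% v 20% | 0.02 | 6.6 | 4.1 | 2.2 |
| 60% v 20% | 0.03 | 8.6 | 5.2 | 2.1 |
| 60% v 20% | 0.05 | 10.8 | 6.3 | 1.4 |

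**6. Masking.** Active hazard 0.03 against placebo 0.02, with 60% of active and 20% of placebo stopping:

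| Model | Difference shown | Difference if both arms stop at 20% |
|---|---|---|
| On drug, no taper | 33.9 − 31.0 = 2.9 | 42.5 − 31.0 = 11.5 |
| On drug, with taper | 6.7 | 11.9 |
| Taper and 30-day window | 12.3 | 14.5 |

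**7. Sensitivity to the assumptions.**
- *Early clustering.* If the hazard halves every 3 days with the same 21-day total, the false difference in step 5 falls to 1.3-2.6 points without the taper and 0.5-0.9 with it.
- *Another dropout model.* Take exponential stopping, no drug taper, retention of 70% v 50% or 80% v 40%, and 21-day event risks of 10-50%. The false difference is 1.2-10.9 points for on-drug events and 1.0-4.1 points with the 30-day window.

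**The case against.** The strongest case against is that crude incidence by arm, with AEs collected for 30 days after the last dose, is a valid description of what happens to subjects given each treatment. Nothing is tested. Discontinuations due to TEAEs are a listed endpoint, and the Kaplan-Meier curve shows time on drug. At 30 per arm, imprecision exceeds every distortion computed above. Pauses may also work against the first mechanism: they follow intolerable withdrawal, so if the drug works, placebo subjects may pause more and gain dosing days. Section 13.1 leaves further analyses to a later SAP that is not in the supplied text.

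Most of this stands, and it sets the severity. Two things temper it:
- The plan manages hypotension and bradycardia by delaying, skipping, reducing or holding doses (Sections 9.5 and 12.1.2). For those events the on-drug columns are the relevant ones.
- The 30-day window does not fully equalise ascertainment. Table 2 gives subjects on schedule AE calls on Days 32, 39 and 46. Section 8.6.1 specifies one 30-day contact for those who discontinue.

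A reader might infer that the plan expects the arms to differ in time on drug. It does not say so: it compares them, without stating a rate or direction. A reader might also take TEAEs to be the designated primary endpoint, but they are one of seven safety endpoints, none named primary.

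**Conclusion.** The gap is real but minor. TEAEs are planned only as crude percentages while exposure is an outcome that can differ by arm, so the contrast for events arising mainly on drug can be distorted either way. Under the assumed stopping and hazards, the size is about 3-6 points for on-drug events with the drug taper counted (5-11 without it) and about 1-2 points if the hazard runs through the 30-day window. Early clustering reduces it further. Every figure rests on assumed rates, and all are below the half-width of about 20 points.

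It would be tempting to conclude that the crude percentages are not comparable, or that an 11.5-point harm would show as 2.9. The documents do not support that. The second figure requires no dosing after a stop and no events after the last dose, whereas the plan provides for a drug taper and collects AEs for 30 more days. With both features the same example shows 12.3 of 14.5 points. The crude table should stay; what is missing is the exposure context beside it.

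**What to change.** In Section 13.4.2.1.1, or in the SAP, keep the crude percentages and add:

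1. Days on study drug by arm, with the number of subjects exceeding 14 days.
2. For any TEAE, severe TEAEs and the cardiovascular events named in the rationale: subjects with a first event per 100 subject-days at risk, with 95% CI. Show separately the on-drug period (including the drug taper, and to Day 27 for subjects who pause) and the post-drug period to 30 days after the last dose. The split keeps rebound hypertension from being assigned only to on-drug time.
3. Optionally, cumulative incidence of first on-drug TEAE by arm, with drug discontinuation as a competing event. Kaplan-Meier censored at drug stop would treat stopping as uninformative, which is doubtful when withdrawal or poor tolerability causes it.

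No test, visit or new data item is needed: AE details, diary dosing and pill counts are already recorded. The cost is SAP wording and a few tables. The rates in item 2 assume a roughly constant hazard within each period, which should be stated with the table.
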